### Additional Information

|   |  |
|---|--|
| Research question and objectives:  | 
This study aims to characterise the use of single-agent olodaterol and single-agent indacaterol, the only marketed long-acting beta2-agonist (LABAs) authorised for chronic obstructive pulmonary disease (COPD), but not for asthma, in clinical practice. Study objectives are as follows:
 
Primary objectives:
 

• Quantify the frequency of off-label use of olodaterol among new users of these medications (i.e., the proportion of new users who do not have COPD)

• Describe the baseline characteristics of new users of olodaterol

 
Secondary objective:
 

• Quantify the frequency of off-label use of indacaterol (a LABA approved for COPD but not for asthma) among new users of these medications (i.e., the proportion of new users who do not have COPD), in order to put into perspective the results for olodaterol initiators

• Describe the baseline characteristics of new users of indacaterol

 |
| Country(-ies) of study:            | The Netherlands, Denmark, and Sweden   |
| Author:                            |  |
| Marketing authorisation holder(s): |  |
| MAH contact person:                |  |
| EU-QPPV:                           |  |
| Signature of EU-QPPV:              | The signature of the EU-QPPV is provided electronically  |

## **2. LIST OF ABBREVIATIONS**

|                  |  |
|------------------|--|
| AMI              | Acute Myocardial Infarction  |
| ATC              | Anatomical Therapeutic Chemical  |
| BI               | Boehringer Ingelheim   |
| BMI              | Body Mass Index  |
| CAT              | COPD Assessment Test   |
| COPD             | Chronic Obstructive Pulmonary Disease  |
| DAMD             | Danish General Practice Database   |
| DDD              | Defined Daily Dose   |
| EMA              | European Medicines Agency  |
| ENCePP           | European Network of Centres for Pharmacoepidemiology and Pharmacovigilance   |
| FEV 1 | Forced Expiratory Volume in 1 Second   |
| GOLD             | Global Initiative for Chronic Obstructive Lung Disease   |
| GP               | General Practitioner or General Practice   |
| ICD              | International Classification of Diseases   |
| ICD-10           | International Statistical Classification of Diseases and Related Health Problems, 10th Revision                        |
| ICD-10-CM        | International Statistical Classification of Diseases and Related Health Problems, 10th Revision, Clinical Modification |
| ICD-9            | International Classification of Diseases, 9th Revision   |
| ICD-9-CM         | International Classification of Diseases, 9th Revision, Clinical Modification  |
| ICPC             | International Classification of Primary Care   |
| ICS              | Inhaled Glucocorticosteroid  |
| LABA             | Long-Acting Beta2-Agonist  |
| LAMA             | Long-Acting Muscarinic Antagonist  |
| mMRC             | Modified British Medical Research Council Questionnaire  |
| NCSP             | Nordic Medico-Statistical Committee Classification of Surgical Procedures  |
| NPR              | National Patient Register (Sweden)   |
| PASS             | Post-Authorisation Safety Study  |
| PHARMO           | Institute for Drug Outcomes Research (the Netherlands); also short for the PHARMO Database Network                     |
| PHARMO-GP        | a data subset of PHARMO Database Network with information from GPs   |
| PPV              | Positive Predictive Value  |

|      |                                    |
|------|------------------------------------|
| PRO  | Patient-Reported Outcome           |
| SABA | Short-Acting Beta2-Agonist         |
| SAMA | Short-Acting Muscarinic Antagonist |
| SD   | Standard Deviation                 |
| WHO  | World Health Organization          |

#### 4. ABSTRACT

|   |  |                                 |  |
|---|--|---------------------------------|--|
| Name of company:
Boehringer Ingelheim GmbH              |  |                                 |  |
| Name of finished medicinal product:
Striverdi, Respimat |  |                                 |  |
| Name of active ingredient:
Olodaterol                   |  |                                 |  |
| Protocol date:
13 Feb 2014                              | Study number:
1222.53  | Version/Revision:
2.0 | Version/Revision date:
14 Oct 2014 |
| Title of study:  | Drug Utilisation Study for Olodaterol  |                                 |  |
| Rationale and background:                                  | Boehringer Ingelheim GmbH (BI) developed olodaterol, an inhaled long-acting beta2-agonist (LABA), for the indication of chronic obstructive pulmonary disease (COPD). LABAs are used in COPD to relieve bronchial constriction and, consequently, to improve symptoms. Because the use of LABAs has been associated with increased morbidity and mortality in patients with asthma, within the “Decentralised Procedure for Striverdi Respimat” the health authorities of the European Union/European Economic Area Member States requested the conduct of a post-approval drug utilisation study to assess potential off-label use of olodaterol in asthma and to characterise the use of olodaterol in clinical practice.  |                                 |  |
| Research question and objectives:                          | 
This study aims to characterise the use of single-agent olodaterol and single-agent indacaterol, the only marketed LABAs authorised for COPD, but not for asthma, in clinical practice. Study objectives are as follows:
 
Primary objectives:
 
 
• Quantify the frequency of off-label use of olodaterol among new users of these medications (i.e., the proportion of new users who do not have COPD)
 
• Describe the baseline characteristics of new users of olodaterol
 
 
Secondary objective:
 
 
• Quantify the frequency of off-label use of indacaterol (a LABA approved for COPD but not for asthma) among new users of these medications (i.e., the proportion of new users who do not have COPD), in order to put into perspective the results for olodaterol initiators
 
• Describe the baseline characteristics of new users of indacaterol
 
 |                                 |  |
| Study design:  | This is a cross-sectional study using information collected in health care databases among new users of olodaterol or indacaterol in the Netherlands, Denmark, and Sweden.   |                                 |  |

|                       |  |
|-----------------------|--|
| Population:    | The source population is all subjects enrolled in the selected study databases at the date olodaterol and indacaterol are available in each database's country. The study groups are those subjects from the source population who receive a first dispensing for single-agent formulations of olodaterol for the primary objective or indacaterol for the secondary objective and have at least 12 months of continuous enrolment in the study databases.   |
| Variables:     | Indication and potential off-label use of olodaterol and indacaterol; characterisation of new users of olodaterol and indacaterol by demographic variables, medical history, and use of other medications.   |
| Data sources:  | The study is planned to be conducted in the following databases: the PHARMO Database Network in the Netherlands, the National Registers in Denmark, and the National Registers in Sweden
A description of each database is provided in Section 9.4; further details from the feasibility report are provided in ANNEX 5. The study will be conducted by using data on drug prescriptions and disease occurrence routinely collected on an ongoing basis for large population-based automated health care databases in the Netherlands, Denmark, and Sweden. |
| Study size:    | Actual counts of numbers of patients using olodaterol in European countries are not yet available since it is not yet marketed in Europe.  |
| Data analysis: | Number and proportion of new users by indication and potential off-label use. Number and proportion of new users according to medical history and use of comedications..   |
| Milestones:    | Start of data collection (contingent on approval, reimbursement, and uptake of olodaterol): 
 
• Denmark: Q1 2015
 
• The Netherlands: Q4 2015
 
• Sweden: Q4 2015
 
 End of data collection: Q1 2018
Interim reports of study results: Q3 2017
Final report of study results: Q3 2018   |

## **5. AMENDMENTS AND UPDATES**

Version 2.0 includes clarification to the milestone table and revision of the primary and secondary study objectives in the context of regulatory review of the protocol.

| Number | Date | Section of Study Protocol | Amendment or Update        | Reason   |
|---------------|-------------|----------------------------------|-----------------------------------|---|
| 1             | 30 Sep 2014 | 6                                | Update of milestones              | Delay in finalization of protocol to respond to regulatory authority review |
| 2             | 30 Sep 2014 | 8                                | Research objectives               | Modified in response to regulatory authority review                         |
| 3             | 30 Sep 2014 | 9.3.4                            | Clarification of primary outcomes | Modified in response to regulatory authority review                         |

## 6. MILESTONES

| Milestone   | Planned Date                                 |
|--|---|
| Start of data collection (expected availability of data on earliest exposure group entry)  : | Denmark: Q1 2015
The Netherlands: Q4 2015
Sweden: Q4 2015 |
| End of data collection (latest possible exposure group entry):   | Denmark: Q1 2018
The Netherlands: Q1 2018
Sweden: Q1 2018 |
| Study progress report(s):  | TBD   |
| Interim report(s) of cumulative study results:   | Q3 2017   |
| Registration in the EU PAS register:   | After regulatory endorsement of the protocol                    |
| Final report of study results from all databases:  | Q3 2018   |

TBD = to be determined. Contact with database custodians is pending.

- 1 Preliminary; dependent on market uptake of olodaterol and contracts with MAH and research partners.
- 2 Considering launch dates and approximately 1-year lag time in database. Launch dates are March 2014 in Denmark, February 2014 in the Netherlands, and August 2014 in Sweden.

## 7. RATIONALE AND BACKGROUND

Chronic obstructive pulmonary disease (COPD) is a serious, chronic disease that affects millions of people worldwide. [P13-02399] COPD typically involves persistent limitation of airflow, a progressive course, and chronically enhanced inflammatory response of the airways to airborne particulates and gases. [P13-02399]

Worldwide, the estimated number of patients with COPD is 63.6 million. [R09-2531] In 2004, the World Health Organization estimated that the European region had approximately 11.3 million patients with prevalent, symptomatic COPD. [R09-2531] A systematic review and meta-analysis of 67 studies conducted in 28 countries between 1990 and 2004 showed that the prevalence of COPD is higher in subjects over 40 years of age than those under 40. The pooled prevalences were 3.1% in subjects under 40 years of age and 9.9% in those 40 years old or older, 8.2% for ages 40-64, and 14.2% for ages 65 years or older. [R06-4117] The health, social, and economic burdens of COPD are predicted to increase in the next several decades because of continuing exposure to tobacco smoke and other risk factors and because of the increasing age of the general populations in many countries. [P13-02399]

Inhaled long-acting beta2-agonist (LABA) drugs are used in COPD and in asthma. At present, the approved indication for the three major LABAs in COPD, formoterol, salmeterol, and indacaterol, is maintenance or long-term use. Formoterol and salmeterol are also approved for use in asthma; for this condition, simultaneous use with corticosteroids is strongly recommended. Within the Decentralised Procedure for Striverdi Respimat, the health authorities of the European Union/European Economic Area Member States requested the conduct of a post-approval drug utilisation study to assess the potential off-label use of olodaterol in asthma patients and to characterise the use of olodaterol in clinical practice.

This protocol is a core protocol describing the study design, methods, and analysis for implementing the study in three European health care databases in the Netherlands, Denmark, and Sweden. This core protocol will need to be adapted to the specifics of each database regarding the type and availability of the recorded information and the coding systems used to record diagnoses and medications.

## **8. RESEARCH QUESTION AND OBJECTIVES**

This study aims to assess the use of single-agent olodaterol in clinical practice. The single agent indacaterol, the only marketed LABA authorised in clinical practice for COPD but not for asthma, will also be assessed. Study objectives are as follows:

Primary objectives:

- Quantify the frequency of off-label use of olodaterol among new users of these medications (i.e., the proportion of new users who do not have COPD)
- Describe the baseline characteristics of new users of olodaterol

Secondary objectives:

- Quantify the frequency of off-label use of indacaterol (a LABA approved for COPD but not for asthma) among new users of these medications (i.e., the proportion of new users who do not have COPD), in order to put into perspective the results for olodaterol initiators
- Describe the baseline characteristics of new users of indacaterol

## 9. RESEARCH METHODS

### 9.1 STUDY DESIGN

This is a cross-sectional study using information collected in health care database(s) among new users of olodaterol or indacaterol in the Netherlands, Denmark, and Sweden. The study period will be 3 consecutive years, with annual cross-sectional descriptions of new users of olodaterol and indacaterol. Evaluation of off-label use and characterisation of new users will be conducted at the **index date**, defined as the date an eligible patient receives the first dispensing of olodaterol or indacaterol.

### 9.2 SETTING

The study is planned to be conducted in the following databases: the PHARMO Database Network in the Netherlands, the National Registers in Denmark, and the National Registers in Sweden. The type of data available in each database is summarised in [Table 1](#). A detailed description of each study database is provided in Sections [9.4](#), [9.4.2](#) and [9.4.3](#).

Table 1 Selected characteristics of the study databases

| Type of Data                    | PHARMO,
the Netherlands         | National
Registers,
Denmark   | National
Registers,
Sweden   |
|--|--|--|---|
| Hospital inpatient discharge diagnoses | Yes  | Yes  | Yes   |
| Hospital inpatient procedures          | Yes  | Yes  | Yes   |
| Hospital/clinics outpatient diagnoses  | No   | Yes  | Yes   |
| General practitioner diagnoses         | Yes, in data subset PHARMO-GP  | Yes, for selected general practices in the Danish General Practice Database  | Yes, for general practices from the counties of Stockholm and Göteborg  |
| Pharmacy-dispensed medications         | Yes  | Yes  | Yes   |
| Prescribed medications                 | Yes in data subset PHARMO-GP   | Yes    | Yes   |

GP = General Practitioner.

1 PHARMO-GP includes approximately 440,000 subjects.

2 The Danish General Practice Database includes approximately 1 million subjects.

3 Population from the counties of Stockholm and Göteborg is about 25% of the total Swedish population

In each country, new users of olodaterol and indacaterol will be identified in the prescription databases, which record information on the medications dispensed in the pharmacies (Figure 1). New users will be characterised in terms of past medical history and use of medications. Past medical history will be evaluated by linkage via unique patient-specific identifiers using the hospitalisation databases, which provide information on hospital and outpatient discharge diagnoses and procedures. Use of medications will be evaluated using the prescription databases. Off-label prescribing will be evaluated for those new users for whom general practitioner diagnoses are available because information from general practitioners is considered the most appropriate for evaluating the indication and potential off-label use of medications.

[figure not shown]

Figure 1 Overall study design

The coding of diagnoses and procedures varies across databases (Table 2). In PHARMO, diagnoses are coded using the *International Classification of Diseases, 9th Revision* (ICD-9); whereas in Denmark and Sweden, diagnoses are coded using the *International Statistical Classification of Diseases and Related Health Problems, 10th Revision* (ICD-10). In PHARMO, procedures are coded using ICD-9 codes; in Denmark, using ICD-10 codes; and in Sweden, using the 2012 Nordic Medico-Statistical Committee's Classification of Surgical Procedures, version 1.16.[\[R14-0443\]](#) The Anatomical Therapeutic Chemical (ATC) classification is used in all three databases to code dispensed medications.

Table 2 Types of diagnosis, procedures, and medication codes in the study databases

| Type of Code | PHARMO, The Netherlands                                   | National Registers, Denmark                      | National Registers, Sweden |
|--------------|---|--|----------------------------|
| Diagnoses    | Hospital: ICD-9
Primary health care: ICPC  | ICD-10
Primary health care: ICPC  | ICD-10                     |
| Procedures   | ICD-9   | ICD-10   | NCSP 1.16, 2012            |
| Medications  | ATC   | ATC  | ATC                        |

ATC = Anatomical Therapeutic Chemical; GP = General Practitioner; ICD-9 = *International Classification of Diseases, 9th Revision*; ICD-10 = *International Statistical Classification of Diseases and Related Health Problems, 10th Revision*; ICPC = *International Classification of Primary Care*; NCSP = *Nordic Medico-Statistical Committee's Classification of Surgical Procedures*.

 Available for PHARMO-GP, a data subset of PHARMO with information from GPs.

### 9.2.1 Source population

The study source population includes all subjects enrolled in the selected study databases at the date olodaterol and indacaterol are available in each database's country.

### 9.2.2 Study period

The start of the study period is at the index date, defined as the dates of the first recorded dispensings of olodaterol and indacaterol in each database. New users of olodaterol and indacaterol will be identified in each of 3 consecutive years, with annual cross-sectional evaluations of off-label use and of characteristics of users.

### 9.2.3 Study groups

Study groups are those subjects from the source population who (1) receive a first dispensing for single-agent formulations of olodaterol or indacaterol and (2) have at least 12 months of continuous enrolment in the study databases preceding the index date. Two study groups will be created: (1) a group of new users of olodaterol and (2) a group of new users of indacaterol.

New users of olodaterol are defined as patients who, with at least 12 months of continuous enrolment before the index date, have their first record of a dispensing for olodaterol. Similarly, new users of indacaterol have their first record of a dispensing for indacaterol in the database (after at least 12 months of continuous enrolment). Patients who receive a dispensing for olodaterol or indacaterol before they meet the criteria of 12 months of continuous enrolment in the database are not eligible to enter the corresponding study groups (olodaterol or indacaterol).

Each group of new users of olodaterol and new users of indacaterol will be divided into two subgroups: (1) LABA naïve in the short term (3 months) and (2) switchers from another LABA. Patients who are LABA naïve in the short term are defined as any new users of olodaterol or indacaterol who did not receive any dispensing for LABAs within 3 months

before the index date. Switchers are defined as any new user of olodaterol or indacaterol who received a dispensing for a different LABA within the 3 months before the index date. Within the olodaterol group and within the indacaterol group, LABA-naïve patients and switchers will be described and compared.

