## 9.7 DATA ANALYSIS

All analyses will be conducted separately in each study database and will be further analysed separately by new users of olodaterol and by new users of indacaterol, further stratified by treatment-naïve subjects and switchers. Analyses will be conducted annually for three consecutive years. Each year will include all patients starting treatment with olodaterol or indacaterol in that specific year. Statistical analyses will be descriptive in nature. Descriptive statistics will include the absolute and relative number of subjects, mean, median, standard deviation, and range for continuous variables. Statistical inference will not be performed (e.g., no *P* values will be generated).

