5.3.2 Health care resource utilisation

Health care resource utilisation will be evaluated within 12 months before cohort entry but not including the index date. The variables listed in [Table 7](#) will be used to capture the utilisation of health care resources. Additional details on the definition of the variables in each data source are described in Section [9.2](#).

Table 7 Health care resource utilisation variables

Health care resource parameter	Definition and categories	Medications included
All dispensings	Number of dispensings for all medications; ordinal variable with 0, 1-9, 10-19, 20 or more	All medications included in Annex Table 1-6
Dispensings for respiratory medications ¹	Number of dispensings for respiratory medications; ordinal variable with 0, 1-4, 5-9, 10 or more	All medications included in the section on respiratory medications in Annex Table 1-6
Dispensings for systemic glucocorticosteroids	Number of dispensings for systemic glucocorticosteroids; ordinal variable with 0, 1-4, 5-9, 10 or more	ATC code H02AB
Dispensings for LABAs	Number of dispensings for LABAs; ordinal variable with 0, 1-4, 5-9, 10 or more	ATC codes R03AC012 (salmeterol) and R03AC013 (formoterol)
Hospitalisations	Number of hospitalisations for any cause; ordinal variable with 0, 1, 2, 3-4, 5 or more	To be determined by each data source
Hospitalisations for COPD	Number of hospitalisations with a primary discharge diagnosis of COPD; ordinal variable with 0, 1, 2, 3-4, 5 or more	ICD-10 codes for COPD: J41-J44, or as defined in Section 5.1 for each data source, but limited to inpatient codes
Hospitalisations for asthma	Number of hospitalisations with a primary discharge diagnosis of asthma; ordinal variable with 0, 1, 2, 3-4, 5 or more	ICD-10 codes for asthma: J45, J46, or as defined in Section 5.1 for each data source, but limited to inpatient codes

ATC = Anatomical Therapeutic Chemical; COPD = Chronic Obstructive Pulmonary Disease; ICD-10 = *International Statistical Classification of Diseases and Related Health Problems, 10th Revision*; LABA = Long-Acting Beta2-Agonist.

¹ Study medications will be counted (e.g., when describing the olodaterol cohort, the dispensings of indacaterol will be counted and vice versa).

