5.3.3 Severity of COPD

Severity of COPD will be evaluated among new users of olodaterol and indacaterol that are aged 40 years or older and have a recorded diagnosis of COPD (with or without a diagnosis of asthma) ever before or up 30 days after the index date. The population aged 40 years or older is considered the most likely to have COPD and is frequently selected in studies to evaluate medication use among patients with COPD [[P07-07347](#), [P11-13226](#), [P07-09136](#)]. Patients aged 39 years or younger with a diagnosis of COPD will still be considered as

Proprietary confidential information © 2017 Boehringer Ingelheim International GmbH or one or more of its affiliated companies

having COPD and described separately if there are at least 5 patients in each COPD severity category. Definitions shown in [Table 8](#) will be adapted to the characteristics and data availability in each data source; database-specific specifications have been described in [Section 9.2](#). The four severity categories will be mutually exclusive, and patients that fulfil criteria for more than one category will be classified as being in the more severe category.

Table 8 Definition criteria of COPD severity (adapted primarily from Verhamme et al., 2012 [[P11-13226](#)])

Severity of COPD	Definition
Mild	Less than two prescriptions/dispensings of drugs for obstructive airways disease of the same class in any 6-month interval in the 12 months before the index date (i.e., 0 or 1 prescriptions/dispensings of the same COPD drug class in the 12 months before the index date, or if ≥ 2 prescriptions/dispensings, these have to be more than 6 months apart)
Moderate	Regular bronchodilator treatment, defined as having at least two prescriptions/dispensings of the same COPD drug class with an interval of ≤ 6 months in the 12 months before the index date ^{1,2}
Severe	Occurrence of at least one of the following events in the 12 months before the index date: 
 • Hospitalisation for COPD exacerbation¹ • At least two COPD exacerbations without hospitalisation, where COPD exacerbation is defined by any of the following³: 
 • A course of antibiotics for lower respiratory tract infection (acute bronchitis or pneumonia)¹ • A course of systemic corticosteroids for the treatment of COPD exacerbation¹ • A diagnoses of COPD exacerbation without hospitalisation

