7. PLANNED ANALYSIS

The different research centres will use the core final study protocol and SEAP to conduct analyses in the respective data sources and generate output that will be provided to the coordinating centre (RTI Health Solutions), which will generate the study reports.

All the analyses will be conducted separately for olodaterol and indacaterol new users and further stratified by LABA-naïve patients and switchers. Analysis for each report (i.e., interim and final) will include data on all patients starting treatment with olodaterol or indacaterol from the start of such treatment during the study period up to the latest available data (see anticipated study periods for interim and final reports in [Table 1](#)). The interim analysis will include all the analyses described in the present section.

Tables and figure shells describing all planned analyses have been developed (see separate Word file) and will be adapted to each data source. For each data source, an attrition table will be generated to describe the impact on the study size at each step of applying the study inclusion and exclusion criteria (Figure Shell 1).

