Annex Table 1-6 (cont'd) Anatomical Therapeutic Chemical codes for comedICATIONS

Medication description	ATC code
Respiratory medications (cont'd)	
Inhaled LABA/ICS	
Salmeterol and fluticasone	R03AK06
Formoterol and budesonide	R03AK07
Formoterol and beclometasone	R03AK08
Formoterol and mometasone	R03AK09
Vilanterol and fluticasone furoate	R03AK10
Formoterol and fluticasone	R03AK11
Salmeterol and budesonide	R03AK12
Inhaled glucocorticosteroid	
Beclometasone	R03BA01
Budesonide	R03BA02
Flunisolide	R03BA03
Betamethasone	R03BA04
Fluticasone	R03BA05
Triamcinolone	R03BA06
Mometasone	R03BA07
Ciclesonide	R03BA08
Fixed combinations of SABAs and SAMAs	ATC codes not available ¹
Fixed combinations of SABAs and ICSs	ATC codes not available ¹
Fixed combinations of LABAs and ICSs	ATC codes not available ¹
Systemic glucocorticosteroids	H02AB
Systemic beta2-agonists	R03CC
Xanthines and fixed dose combinations of xanthines with adrenergics	R03DA, R03DB
Roflumilast	R03DX07
Nasal glucocorticosteroids	R01AD
Omalizumab	R03DX05
Leukotriene receptor antagonists	R03DC
Cromoglicic acid	R03BC01
Nedocromil	R03BC03

Proprietary confidential information © 2017 Boehringer Ingelheim International GmbH or one or more of its affiliated companies

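### The plan's coded LABA lists hold only single-agent salmeterol and formoterol, so the LABA dispensing count omits other LABA products and the naïve/switcher split has no usable code list

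*Protocol*

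**What the plan says.** Protocol 9.2.3 divides each new-user group into "LABA naïve in the short term (3 months) and (2) switchers from another LABA". Naïve patients are "any new users of olodaterol or indacaterol who did not receive any dispensing for LABAs within 3 months" before the index date. A switcher is a new user who "received a dispensing for a different LABA within the 3 months before the index date". The section restricts the index drugs to single-agent formulations. It puts no such limit on the prior LABA and cites no code list.

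SAP Section 7 applies the split widely: "All the analyses will be conducted separately for olodaterol and indacaterol new users and further stratified by LABA-naïve patients and switchers". The SAP text does not restate the definition or the 3-month window. Protocol 9.7 calls the first group something else: "further stratified by treatment-naïve subjects and switchers".

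The one variable that gives LABA codes in the body of either document is the resource-use count. SAP Table 7 (Section 5.3.2) defines it by "ATC codes R03AC012 (salmeterol) and R03AC013 (formoterol", and Protocol 9.3.3.7 uses the same two codes. Combinations such as "Salmeterol and fluticasone" stand in SAP Annex Table 1-6 under their own LABA/ICS heading.

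**The concern.** A stratum applied to every analysis needs a definition that separate research centres will program in the same way. Here the controlling term has no codes attached, and the lists a programmer would turn to are incomplete for the purpose. They omit the combinations, and they misplace or omit the two study drugs.

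Two results are at stake. The first is the LABA resource-use row, which follows its printed codes. The second is the contrast between naïve patients and switchers, which Protocol 9.2.3 says will be described and compared. The study was requested because of possible use in asthma, and Protocol Section 7 notes that, for the LABAs approved in asthma, simultaneous corticosteroid use is strongly recommended. Readers may therefore look for patients who moved from a LABA/ICS to a single-agent LABA, and the plan does not say which stratum they are in.

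**Working it through.** No arithmetic in the plan bears on this point. The check sets the LABA lists side by side and then applies them.

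**Step 1. What each list contains**

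| Place | Contents |
|---|---|
| Protocol 9.3.3.7, LABA dispensings | R03AC012 (salmeterol), R03AC013 (formoterol) |
| SAP Table 7, LABA dispensings | The same two codes |
| Protocol Annex Table 4:2, inhaled LABAs | R03AC12, R03AC13 |
| SAP Annex Table 1-6, inhaled LABAs | R03AC12, R03AC13 |
| Both annexes, inhaled SABAs | Includes indacaterol, R03AC18 |
| Both annexes, all headings | Olodaterol, R03AC19, is absent |
| Protocol Annex Table 4:2, LABA/ICS | Separate class, found by national drug code |
| SAP Annex Table 1-6, LABA/ICS | Separate class, R03AK06 to R03AK12 |
| SAP 5.3.3, drug classes for severity | LABA/ICS grouped with inhaled glucocorticosteroids |

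Filing indacaterol under SABAs conflicts with Protocol Section 7, which names it as one of three major LABAs in COPD. Table 7 and Protocol 9.3.3.7 also print the two codes with an extra zero compared with the annexes.

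**Step 2. The Table 7 count**

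This follows directly from the printed codes. A patient whose only LABA-containing product in the 12 months before index was a LABA/ICS falls in the category 0, however many packs were dispensed. So does a patient whose only prior LABA was the other study drug. The Table 7 footnote that counts study medications is attached to the respiratory-medication row, not the LABA row. The error runs one way: for any patient, the printed count is at or below the count of all LABA-containing products.

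**Step 3. The naïve/switcher split**

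This depends on what LABA means in Protocol 9.2.3.

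| Prior LABA history | If the coded list is used | If any LABA-containing product counts |
|---|---|---|
| Single-agent salmeterol or formoterol within 3 months | Switcher | Switcher |
| Only LABA/ICS within 3 months | Naïve | Switcher |
| Only the other study drug within 3 months | Naïve | Switcher |
| Last LABA of any kind more than 3 months before | Naïve | Naïve |

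The second and third rows are where the readings diverge. The third row is a real possibility, since SAP 6.3 lets a patient enter both drug groups. The fourth row is the same under both readings and follows from the stated window.

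**Step 4. Size**

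Let *a* be the share of new users with single-agent salmeterol or formoterol within 3 months, and *c* the share whose only LABA product in that time was a LABA/ICS or the other study drug. Under the list reading, switchers are reported as *a* instead of *a* + *c*, and *c*/(1 − *a*) of the naïve stratum had a LABA within 3 months. The documents give neither *a* nor *c*.

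**Step 5. The primary outcome**

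SAP 7.5.1 classifies patients by age and by recorded COPD and asthma diagnoses. LABA history plays no part, so overall off-label prevalence is the same under either reading.

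**The case against.** The strongest reply is that the coded lists were written for other variables, resource use and comedication, and that Protocol 9.2.3 points to none of them. Its wording can cover a LABA given in a combination. The lists are also poor candidates for the switcher rule, since using them would make a move from indacaterol to olodaterol a naïve start. In addition, SAP 5.3.2 and 6.1 send database-specific definitions to Section 9.2, which is not in the available SAP text, and the table shells are a separate file. Explicit codes may sit there. This stands. A reader might infer that LABA/ICS patients are analysed as naïve and that switchers are undercounted, but the documents support that as one reading only.

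A reader might also see a flaw in the 3-month window itself, or a contradiction with SAP Table 8, which treats as regular treatment two dispensings of one class "with an interval of ≤ 6 months in the 12 months before the index date". Neither holds. The protocol discloses the window in the group's name and does not claim to isolate first-ever LABA starts. Table 8 grades COPD severity, and its bronchodilator class pools short- and long-acting agents, so a patient on regular salbutamol can correctly be LABA-naïve. Protocol 9.7.4 ties switchers back to Section 9.2.3, so treatment-naïve is loose labelling and not a second definition.

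Finally, the comedication tables cover 12 months, list LABA/ICS separately and are split by stratum, so they would show how much of the naïve group had such a product. That helps in part. They do not separate the last 3 months from months 3 to 12, and they cannot give off-label prevalence by actual switch status.

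The reply does not reach the Table 7 row, whose codes are printed, or the placing of indacaterol under SABAs.

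**Conclusion.** The point holds as a code-list defect with two consequences of different certainty. As printed, the LABA dispensing count omits LABA/ICS and study-drug LABA dispensings. This needs no inference, with the one reservation that Section 9.2 may adapt the row by database. The naïve/switcher split has no codes, and the only coded LABA list cannot support it. Misclassification of patients coming from a LABA/ICS or from the other study drug is conditional on that list being used.

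The effect is confined to the stratified results and the resource-use row. The overall off-label prevalence does not change. No magnitude can be given: any percentage would rest on assumed shares of prior LABA and LABA/ICS use for which the documents offer no basis. The correction should be made because it is specific and costs almost nothing.

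**What to change.** 1. In the SAP, define LABA once, for both the Table 7 row and the naïve/switcher split, as any LABA-containing product: R03AC12, R03AC13, R03AC18 and R03AC19 (excluding the patient's own index drug), R03AK06 to R03AK12, and other LABA fixed combinations found by national drug code. Remove the extra zero from the Table 7 codes.
2. In Annex Table 1-6, move indacaterol from the SABA to the LABA heading and add olodaterol there. SAP 5.1 relies on the same annex for the LABA component of probable COPD, so that description benefits too.
3. Report switchers from a single-agent LABA and switchers from a LABA/ICS separately.
4. Restate the definition in the SAP and use the label LABA-naïve in the short term (3 months) throughout, in place of treatment-naïve.
5. Optionally, add a descriptive sensitivity split by any LABA use in the 12 months before index, which the enrolment requirement already covers. This is a preference and not needed to correct the defect.

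The cost is a code-list edit and a few extra table rows, using data the plan already requires. The downside is slightly smaller subgroups. If Section 9.2 already contains such a list, a cross-reference from Section 7 and alignment of Table 7 and the annex would be enough for the definition itself.
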